### **9.3.10. Exposure/treatment**

Information on TACE to be documented:

- Date of administration
- Embolization agent
- Drug name

Information on sorafenib to be documented:

- Start date of treatment
- Prescribed dose
- Frequency of daily intake
- Date and details on dose adaptations
- Dates and details on treatment interruptions
- Date of permanent stop of treatment
- Reason(s) for interruptions or stop of treatment

Information on other systemic treatments to be documented:

- Start date of treatment
- Drug name or tick for "investigational drug"
- Stop date of treatment

### **9.3.11. Reasons for choice of treatment**

The treating physician will decide on the treatment of the patient based on his medical assessments in close relation to the patient's physical and psychological status. All treatment decisions will follow the real-life treatment behavior of the physician. As there can be expected a wide range of factors influencing treatment decisions over the entire observation period, this will not be captured on the CRF in detail. In any case reasons for stop of sorafenib will be documented.

## **9.4. Data sources**

The investigator collects historic data (demographic and clinical characteristics) from medical records if available. Likewise, the investigator collects treatment related data, results of tumor assessments and other disease status information, also documented in the medical record, during visits that take place in routine practice. For any adverse events that occur, information is directly obtained from the patient. In case a patient is seen by more than one physician for his/her disease (e.g. the patient is monitored by a physician other than the initial investigator), the initial investigator should make every effort to collect information on any visits (including results) that have taken place outside the investigator's site

due to the patient's disease, for example by interviewing the respective physician or patient or by obtaining an accompanying letter with detailed information and results.

## **9.5. Study size**

The primary objective of the study is the comparison of two cohorts (i.e. cohort 1: patients with early start of Sorafenib treatment vs. cohort 2: patients without early start of Sorafenib treatment) regarding overall survival as defined in Section 9.7.4. The enrollment period is planned to be 18 months with a minimum follow-up period of 18 months resulting in total study duration of 36 months. In order to achieve approximately 1,500 patients who have a complete documentation, it is envisaged to enroll 1,670 patients accounting for an expected loss to follow up rate of approximately 10%.

It is expected that out of the 1,500 completely documented patients at least 250 will become part of cohort 1 (patients with early start of Sorafenib treatment) while at least the same number of patients will become part of cohort 2 (patients without early start of Sorafenib treatment). Further assuming a prolongation of median survival time from 9 to 12 months in patients with early start of Sorafenib treatment, exponential distribution of overall survival, equal cohort sizes of 250 patients, no loss of patients for evaluation due to poor overlap of the cohorts' propensity score distributions, 18 months of enrollment, and a total study duration of 36 months, a power of 83% can be achieved in a one-sided log-rank test with type I error rate alpha of 2.5%. SAS® PROC POWER, version 9.2, has been used for power calculation.

## **9.6. Data management**

The investigator collects historic data (demographic and clinical characteristics) from medical records if available. Likewise, the investigator collects treatment related data during visits that take place in routine practice.

A global Contract Research Organization (CRO) will be selected and assigned for EDC system development. The CRF will be part of the EDC system which allows documentation of all outcome variables and covariates by all participating sites in a standardized way. Information on the EDC system is available upon request. The respective document is listed in Annex 1.

Each patient is identified by a unique central patient identification code. This code is only used for study purposes. The patient code consists of a combination of a country code, site number and patient number. For the duration of the study and afterwards, only the patient's investigator is able to identify the patient based on the patient identification code.

For information on quality control, refer to section 9.8

## **9.7. Data analysis**

### **9.7.1. Statistical considerations**

All variables will be analyzed descriptively with appropriate statistical methods: categorical variables by frequency tables (absolute and relative frequencies) and continuous variables by sample statistics (i.e. mean, standard deviation, minimum, median, quartiles and maximum). Continuous variables will be described by absolute value and as change from baseline per analysis time point, if applicable.

All analyses will be performed for the total study population (overall analysis) and separately for each study region. In addition, country-specific analyses might be performed, if patient numbers are sufficient and analyses are required for local reasons. Patients receiving at least one TACE will be included in the analysis. Whenever reasonable, data will be stratified by subgroups (e.g. age, gender, baseline characteristics).

Sample size and disposition information by analysis time point will be displayed in a frequency table.

All therapies documented will be coded using the World Health Organization – Drug Dictionary (WHO-DD). Medical history, any diseases and AEs will be coded using the latest Medical Dictionary for Regulatory Activities (MedDRA) version. In addition Adverse Events will be coded according to the Common Terminology Criteria for Adverse Events (CTCAE) Version 4.03.

All statistical details including calculated variables and proposed format and content of tables will be detailed in the Statistical Analysis Plan (SAP). The SAP will be finalized before study database lock. The SAP is available upon request. The respective document is listed in Annex 1.

It is planned to have the first interim analysis after 500 patients observed for at least 6 months. This first interim analysis was conducted on 26th February 2015. This analysis did not include the formal comparison of the two cohorts of special interest, as planned. Based on results of the 1st interim analysis, the second interim analysis is planned after approximately 1000 patients have been observed for at least 6 months, in order to evaluate patient sample size and feasibility for conducting the propensity score analysis. This analysis will not include the formal comparison of the two cohorts of special interest. The final analysis will be performed after end of the study, which is the date after which subjects will have been in the study for 18 months, or have been lost to follow-up or have died.

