### 9.1.1. Primary endpoint(s)

The primary endpoint is overall survival (OS) from time of TACE non-eligibility.

OS is defined as the time interval from TACE non-eligibility to death due to any cause. Patients alive at the end of study will be censored at the last date known to be alive.

A patient is classified non-eligible for TACE, if at least one of the criteria in 9.3.8 except ‘advanced liver disease (Child-Pugh class B or C) is met.

Time of TACE non-eligibility is the first point in time in the study when TACE non-eligibility is met according to the documentation in the CRF. In case of a pre-existing TACE non-eligibility, time of TACE non-eligibility will be defined as the time of enrollment.

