## **9.2. Setting**

### **9.2.1. Eligibility**

Patients enrolled in this study have a diagnosis of unresectable HCC in whom a decision to treat with TACE has been made at time of study enrollment.

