### **9.2.2. Inclusion criteria**

- Patients with histologically/cytologically documented or radiographically diagnosed HCC. Radiographic diagnosis needs typical findings of HCC by radiographic method i.e. on multi-dimensional dynamic CT, CT hepatic arteriography (CTHA)/CT arterial portography (CTAP) or MRI.
- Patients with BCLC stage B or higher.
- Patients in whom a decision to treat with TACE has been made at time of study enrollment. Patients that have received one TACE in the past also can be enrolled, if the TACE was done at the same site and all required data about such previous TACEs are available. TACE

includes both conventional TACE with lipiodiol (or similar agents) and chemotherapeutic agent(s) and TACE with DC Beads® excluding TAE without chemotherapeutic agent.

- Patients with unresectable HCC (incurable with curative treatments including resection or ablation or not eligible for resection or local ablation)
- Patients must have signed an informed consent form
- Patients must have a life expectancy of at least 8 weeks

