### **9.3.8. Disease status summary**

The following criteria will be assessed at initial visit and every follow-up visit:

- lack of portal blood flow (because of portal vein thrombosis, portosystemic anastomoses or hepatofugal flow)
- Patients with lobar or segmental portal vein thrombosis.
- Patients with advanced liver disease (Child–Pugh class B or C)
- Clinical symptoms of end-stage cancer
- Extrahepatic spread (N1, M1)
- ECOG PS  $\geq 1$
- BCLC C or D
- Vascular invasion.
- Two or more consecutive incomplete necrosis (depositions (50%) of lipiodol) are seen by response evaluation CT within the treated tumors at the 4 weeks after adequately performed TACE. (excluded from initial visit)
- Two or more consecutive appearances of a new lesion (recurrence) are seen in the liver by response evaluation CT at the 4 weeks after adequately performed TACE. (excluded from initial visit)
- TACE failure by investigator’s assessment (excluded from initial visit)
- Clinical encephalopathy
- Refractory ascites
- Hepatorenal syndrome
- Extensive tumor with massive replacement of both entire lobes
- Technical contraindications to hepatic intra-arterial treatment
- Renal insufficiency (creatinine  $\geq 2$  mg/dL or CrCl  $< 30$  mL/min)
- Other (to be specified)

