#### **9.7.5. Analysis of secondary outcome(s)**

The secondary efficacy endpoints will be analyzed for the two cohorts described below

- Overall: Includes all patients who were treated with at least one TACE
- Sorafenib: Includes all patients who were treated with sorafenib

or for the two cohorts of special interest, as applicable.

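### For patients enrolled before any TACE and already non-eligible, the primary OS clock starts at enrolment but inclusion requires a later TACE, so survival up to that TACE is guaranteed

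*Protocol*

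**What the plan says.** Four rules in the protocol meet here.

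- **Entry (9.2.1, 9.2.2).** The main route is "Patients in whom a decision to treat with TACE has been made at time of study enrollment", so the TACE is decided but need not have been given. A second route admits patients with one TACE already done: "Patients that have received one TACE in the past also can be enrolled".
- **Non-eligibility at entry (9.3.8, 9.2.2).** The criteria are scored from the start: "The following criteria will be assessed at initial visit and every follow-up visit". Only three of them, all concerning earlier TACE, are left out at the initial visit. The list includes BCLC C or D, ECOG PS of 1 or more and vascular invasion, while the inclusion criterion is "Patients with BCLC stage B or higher". A patient can therefore enter already non-eligible.
- **Time zero (9.1.1).** "In case of a pre-existing TACE non-eligibility, time of TACE non-eligibility will be defined as the time of enrollment".
- **Analysis set (9.7.1).** "Patients receiving at least one TACE will be included in the analysis". Section 9.7.5 repeats the condition for the overall cohort: "Overall: Includes all patients who were treated with at least one TACE".

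Elsewhere the first TACE is the natural start: 9.2.5 counts each patient's observation from it, and 11.2 begins adverse event collection with it.

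**The concern.** An analysis set should be fixed by what is known at time zero. For a patient enrolled before any TACE and already non-eligible, the qualifying TACE comes after time zero. If that patient dies or deteriorates first and the TACE is never given, the patient drops out of the set. Those who stay in are known to have survived the wait. This is immortal time, produced by the stated rules.

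Two things are at stake. The Kaplan-Meier curves from TACE non-eligibility (9.7.4) look better than the survival of the patients they claim to describe. In addition, if the guaranteed interval is spread unevenly over the two cohorts, the primary hazard ratio absorbs the difference. Other endpoints counted from TACE non-eligibility (8.2) inherit the same start. Survival from initial TACE (9.1.2) does not, because its clock begins at the qualifying event.

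**Working it through.** **Who is affected**

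| At enrolment | Time zero for primary OS | At-least-one-TACE condition met | Guaranteed time |
|---|---|---|---|
| Non-eligible, no TACE yet | Enrolment | After time zero | Enrolment to first TACE |
| Non-eligible, one TACE already done | Enrolment | Before time zero | None |
| Eligible, non-eligible after a TACE | When a criterion is first met | Before time zero | None |

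**Inputs from protocol 9.5.** Exponential survival, medians 12 months (cohort 1) and 9 months (cohort 2), so the hazard ratio is 9/12 = 0.75. There are 250 patients per cohort, 18 months of enrolment, 36 months in total and a one-sided alpha of 2.5%.

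**The plan's own figure.** Expected deaths per cohort are 250 × [1 − (e^(−18λ) − e^(−36λ))/(18λ)], with λ = ln 2/median. This gives 195.0 + 216.2 = 411.2. Power is Φ(√411.2/2 × |ln 0.75| − 1.96) = 83.1%, against the stated 83%. The planning figure is correct and is not in dispute.

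**Inputs the protocol does not give.** These are the share q of a cohort that is affected and the wait g from enrolment to first TACE. Both are assumed: q from 25 to 75% and g from 2 to 6 weeks, with wider values in places to show sensitivity.

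**Deaths removed among affected patients.** The share is 1 − 2^(−g/median). Four weeks is 28/30.44 = 0.92 months, so cohort 2 loses 1 − 2^(−0.92/9) = 6.8%.

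| Wait | Cohort 1 | Cohort 2 |
|---|---|---|
| 1 week | 1.3% | 1.8% |
| 2 weeks | 2.6% | 3.5% |
| 4 weeks | 5.2% | 6.8% |
| 8 weeks | 10.1% | 13.2% |

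These are upper bounds if the 8-week life-expectancy criterion (9.2.2) keeps early deaths low.

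**Effect on the hazard ratio, unstratified Cox.** An affected patient has zero hazard up to g and the protocol's exponential hazard afterwards. Censoring is uniform between 18 and 36 months. The large-sample Cox score equation was solved numerically.

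*Affected patients in cohort 2 only, true HR 0.75:*

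| Share of cohort 2 | 2 weeks | 4 weeks | 6 weeks |
|---|---|---|---|
| 25% | 0.757 | 0.764 | 0.771 |
| 50% | 0.764 | 0.778 | 0.793 |
| 75% | 0.771 | 0.793 | 0.815 |

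The shift runs from 0.757 − 0.75 = 0.007 to 0.815 − 0.75 = 0.065. On the same grid a true 1.00 becomes 1.01 to 1.10. If 25% of cohort 1 is affected as well, the middle cell falls from 0.778 to 0.764.

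*Both cohorts affected:*

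| Setting | True 0.75 | True 1.00 |
|---|---|---|
| Same share (30 to 100%) and same wait (1 to 8 weeks) | 0.750 to 0.752 | 1.000 |
| 60% in each; cohort 1 waits 2 weeks, cohort 2 waits 4 | 0.767 | 1.025 |
| 60% in each; cohort 1 waits 4 weeks, cohort 2 waits 2 | 0.734 | 0.976 |
| 30% of cohort 1, 60% of cohort 2, 4 weeks | 0.767 | 1.025 |
| 60% of cohort 1, 30% of cohort 2, 4 weeks | 0.734 | 0.976 |

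**With propensity strata.** Section 9.7.4 plans equally sized strata with inverse-variance pooling. A large-sample simulation used five strata, the same wait in both cohorts, and a score containing zero-previous-TACE status plus one other covariate. With affected patients in cohort 2 only, it gives about 0.75 to 0.77 for a true 0.75 and 1.00 to 1.01 for a true 1.00. Strata balance shares, not waits: with 60% affected in each cohort and waits of 2 and 4 weeks, stratification leaves the shift where it was.

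**The case against.** The strongest reply is that the TACE condition binds both cohorts alike, so the hazard ratio need not move, and that the planned analysis is not an unstratified Cox model. Section 9.7.8 lists number of previous TACE as a possible confounder. Counted at time zero, the affected patients are exactly those with none. If they sit only in cohort 2, they fall into strata with few or no cohort 1 patients and carry little weight. If both cohorts contain them, like is compared with like. This stands, with two limits: 9.7.8 does not say at which time the count is taken, and a difference in waits is not removed.

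It is also fair that the wait may be only days once TACE is decided, that the life-expectancy criterion and the exclusion of hospice patients lower early deaths, and that TACE-treated patients are the intended population. These points bear on size. They do not explain why the clock starts before the patient belongs to that population.

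A reader might go further and infer that cohort 2 survival is overstated and the hazard ratio shifted against early sorafenib, because TACE is the decision required for entry and 9.2.3 excludes systemic therapy before the first TACE. The documents do not support that as a conclusion. Section 9.7.4 lets a patient be in cohort 1 whether or not TACE continues. Table 2 in 9.3 schedules the decision on further treatment at follow-up visits only, so the cohort of these patients is not settled. Nothing is said about how long either cohort waits. Nor is it right that propensity stratification is powerless here.

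**Conclusion.** The point holds for patients who are TACE-naive at enrolment and already non-eligible, and for no others. For them, 9.1.1 and 9.7.1 together guarantee survival from enrolment to first TACE, and nothing in the protocol removes that interval. The statistical analysis plan is not at hand and may deal with it, but the protocol fixes both rules as they stand.

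The certain effect is on absolute survival, which is raised in each cohort that contains such patients. Bias in the hazard ratio is conditional. It is at most 0.002 if share and wait are alike. It is about 0.01 to 0.07 in an unstratified model at a true 0.75, if 25 to 75% of one cohort is affected with waits of 2 to 6 weeks. It is smaller after stratification on number of previous TACE. Its direction is open. Shares and waits are assumptions, and the early hazard is the protocol's exponential one. This is an inexpensive correction worth making, not evidence that the primary result would be wrong.

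**What to change.** In 9.1.1, state that for patients with pre-existing non-eligibility and no TACE before enrolment, time zero is the later of enrolment and first TACE, for the survival clock and for cohort assignment. Covariates for the propensity score should be taken at the same point. The at-least-one-TACE condition is then met at or before time zero for every patient, and the guaranteed interval disappears from both curves and from the hazard ratio. Delayed entry into the risk set at first TACE is an acceptable alternative.

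Report by cohort the number of affected patients and their wait from enrolment to first TACE. Report also how many enrolled patients never received a TACE, and why.

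The cost is one sentence in 9.1.1 and a few table rows. The TACE date is already collected (9.3.10). A few weeks of survival time are not counted for these patients. The 9.7.4 exclusion for systemic treatment before time zero must be read against the new date. That should change little, because 9.2.3 already excludes systemic therapy before the first TACE.

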#### **9.7.2. Analysis of demography, disease details, prior and concomitant medication and other baseline data**

All background data such as patient demographics, diagnosis and prior treatment of HCC, past medical history, concomitant diseases, and concomitant medication will be described by presenting frequency distributions and/or basic summary statistics.

#### **9.7.3. Analysis of treatment data**

Statistical summaries will be provided by cohort summarizing for duration of exposure to TACE treatment. Duration of TACE treatment is defined as the time interval from of the first TACE to the date of permanent discontinuation of TACE (when an investigator decides no longer TACE is applicable regardless of the reason for discontinuation including death).

In addition, for patients treated with sorafenib, duration of exposure to Sorafenib will also be provided.

Duration of exposure will be calculated in person time.

#### **9.7.4. Analysis of primary outcome(s)**

The primary efficacy endpoint is Overall Survival (OS). It is defined in this study as the time (days) from time of TACE non-eligibility to death due to any cause. Patients lost to follow-up or alive at the end of the study will be censored at the last date known to be alive.

For statistical evaluation, two patient cohorts of special interest will be compared regarding the primary endpoint. These two cohorts are defined as:

- Cohort 1: Patients with early start of Sorafenib treatment. This cohort comprises all patients where the physician decides at the time of TACE non-eligibility to choose Sorafenib as the next treatment option (regardless of whether TACE treatment is continued or not).
- Cohort 2: Patients without early start of Sorafenib treatment. This cohort comprises all patients where the physician decides at the time of TACE non-eligibility not to choose Sorafenib as the next treatment option.

This cohort also includes patients with TACE non-eligibility for whom the decision to treat with Sorafenib is made at a later points in time, patients who are never treated with Sorafenib as well as patients for whom another systemic cancer treatment has been chosen by the physician either at time of TACE non-eligibility or at a later point in time.

According to the definition of the two cohorts, patients where no TACE non-eligibility occurred during the study do not qualify for this analysis. In addition, patients treated with Sorafenib or any other systemic anti-cancer treatment prior to time of TACE non-eligibility are excluded from this analysis. These groups will be described separately.

As part of the descriptive analysis, Kaplan-Meier (KM) estimates for OS will be displayed for the two patient cohorts of special interest.

In an effort to deal with confounding typically present in non-randomized studies, a stratified propensity score approach will be applied for further evaluation. This approach is undertaken with the intention to create strata containing patients in both treatment cohorts for which background variables (covariates) are balanced. The propensity score model will be determined based on variables potentially affecting the treatment decision at time of TACE non-eligibility as well as other variables potentially related to the outcome. Balance of covariates (including important interactions) within each stratum will be investigated, and the propensity score will be re-estimated, as necessary, until adequate balance is demonstrated. All of this will be done in an outcome-blinded manner. Assuming that adequate balance is achieved, equally sized strata will be determined based on the resulting final propensity scores. Within each stratum, the stratum-specific hazard ratio will be estimated based on the applied Cox-model. Subsequently, an overall hazard ratio estimate as well as the corresponding 95%-confidence interval will be calculated based on the stratum-specific estimates applying inverse variance-weighting. Further details will be given in the SAP.

